#### 24hour Randomisation:

Web: https://lictr.leeds.ac.uk/webrand/

Please ensure that you have completed the following eCRFs immediately after randomisation:

- Consent Form
- Eligibility Checklist
- Baseline assessment
  - Randomisation

A copy of the consent form should also be sent via the CTRU's secure file transfer service (SFTS). The HRQoL baseline questionnaire and the baseline neurocognitive function tests must be sent to the CTRU immediately after randomisation

Confirmation of randomisation, including details of treatment allocation, will be emailed automatically to the PI and research team once complete.

Following randomisation, a paper F50 Contact Details CRF should be collected and sent to CTRU via the SFTS, to confirm the participant's and primary caregiver's preferred method of questionnaire administration and completion after randomisation. Applicable contact details, email address/mobile phone number will be collected on the F50 Contact Details CRF as appropriate.

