### 3 Trial design overview

APPROACH is a phase III UK multi-centre, open-label RCT with multi-staged assessments. The two-arm RCT of PBT vs. photon RT in patients with ODG, will assess whether good prognosis ODG patients treated with PBT have better NCF in comparison to those treated with standard photon RT. Neurocognitive function will be assessed at baseline, one month post end of RT and at each annual follow-up.

A total of 246 patients will be randomised 1:1 between PBT and photon RT, with PBT being delivered in one of the two NHS PBT centres and photon RT being delivered in the local RT centre. For those randomised to PBT, during PBT, the participant will be under the care of the clinician in the PBT centre, who will be responsible for their RT planning, prescription and delivery. For those randomised to photon RT, during photon RT, the participant will be under their radiotherapy planning, prescription and delivery. In the lead up to RT (PBT or photon RT), during adjuvant chemotherapy and during follow up, the participant will be under the care of the clinician in the local centre. Following radiotherapy, all patients will receive adjuvant PCV chemotherapy, with clinical review and chemotherapy toxicity recorded at each cycle.

Follow up will be as standard of care, with trial-specific assessments at baseline, weekly during RT and at 1, 3, 6, 12, 24, 36, 48 and 60 months post end of RT. Secondary endpoints also include additional NCF outcomes, HRQOL, endocrinopathy, treatment compliance, work and cost impact, caregivers distress, early and late toxicity, response assessment, progression free survival (PFS) and overall survival (OS).

There are four stages of assessment to ensure trial continuation is warranted throughout. Recruitment will take place in 18-25 centres over 3/2 years.

• Stage 1: (internal pilot phase) will confirm feasibility of recruitment over the first 12 months. If successful, the trial will continue to full recruitment and Stage 2 assessment.

• Stage 2: an interim analysis of NCF at 2 years as an intermediate endpoint for early signs of efficacy will be performed once all patients reach  $\geq$ 2-year follow-up. If positive there is the potential to recommend change in practice; trial follow-up will continue regardless for longer term outcomes.

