#### 6.3 Training requirements for site staff

All site staff must be appropriately qualified by education, training and experience to perform the trial related duties allocated to them, which must be recorded on the site authorised personnel log (APL).

CVs for all staff must be kept up-to-date, signed, dated and copies (or statement of their location) held in the Investigator Site File (ISF) held at site. An up-to-date, signed copy of the CV for the PI must be forwarded to the CTRU prior to site activation.

Good clinical practice (GCP) training is required for all staff responsible for trial activities. The frequency of repeat training may be dictated by the requirements of their employing institution, or 2 yearly where the institution has no policy, and more frequently when there have been updates to the legal or regulatory requirements for the conduct of clinical trials. Evidence of current GCP training for the PI must be forwarded to the CTRU prior to site activation.

Training in the administration of NCF tests is required for all staff responsible for conducting these tests. These staff may be research nurses or other assigned healthcare professionals. Refresher training must be completed annually and will also be required after a period of inactivity. Evidence of completion of training in the administration of NCF tests for site staff who will conduct these tests must be forwarded to the CTRU prior to site activation. For further information related to NCF test administration please refer to the **APPROACH NCF Test Administration Guidelines**.

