#### 9.10 Neurocognitive function tests

The full battery is described below, together with the domains assessed. The full battery will be performed at baseline (before randomisation), 1 month post-end of RT and at 12, 24, 36, 48 and 60 months post-end of RT.

Baseline testing must be completed before randomisation.

Those tests that contribute to the primary endpoint assessment are those included in the EORTC core clinical trial battery composite (CTB COMP), an internationally recommended (van den Bent *et al.* 2011; Wefel *et al.* 2011) for use in studies of NCD in cancer patients.

CTB COMP tests consist of:

- Hopkins Verbal Learning Test-Revised (HVLT-R)
- Trail Making Test A and B (TMT-A/B)
- Controlled Oral Word Association test (COWA)

Cognitive test	Description	Time
Hopkins Verbal Learning	12 words are read aloud to the patient	10 minutes, plus 5
Test-Revised	with 2 second intervals. Direct recall is scored for trials 1-3. After a 20-25 minute interval, delayed recall (trial 4) and recognition is scored	minutes

Trail Making Test Part A	Circles labelled 1 through 25 to be connected as fast as possible	2-3 minutes
Trail Making Test Part B	Circles labelled 1-13 and A-L to be connected in alternating successive order (i.e., 1-A, 2-B, etc.) as fast as possible	5 minutes
COWA	Naming as many words as possible starting with a certain letter within 1 minute	6 minutes

CTB COMP tests cover assessment of processing speed, verbal memory, and executive functioning. Tests within CTB COMP must be administered by a trained individual (see **NCF Test Administration Guidelines)** in a face-to-face setting, in a quiet uninterrupted environment (e.g. separate clinic room).

Specific NCF test forms will be provided for the completion of these tests. The printed text must not be altered in any way. Completed NCF test forms should be scanned and returned to the CTRU via the APPROACH trial specific secure file transfer service (SFTS) within 28 days of completion for QA and scoring purposes.

Training to perform the NCF tests for the primary endpoint will be delivered as part of the site initiation process. A yearly refresher of the training will be provided. More frequent refresher training may be required if any concerns are raised during the NCF QA review of completed NCF test forms. Further information related to training can be found in the **NCF Test Administration Guidelines**.

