QA will be undertaken centrally through visual inspection of the raw data, ensuring that any issues with reliability and validity of assessments is recorded. Appropriate feedback to centres will be provided.

Additional tests are also included at each time point to allow a more thorough neurocognitive assessment. Additional tests will contribute to secondary NCF endpoints and will be assessed using the online electronic platform, CNS Vital Signs. Instructions regarding the execution of CNS Vital Signs will be provided. Participants will complete the electronic assessments after completing the CTB COMP tests above. These can be completed on a desktop in a quiet undisturbed environment, and must be completed under the supervision of a Research Nurse or other trained individual.

Cognitive test	Description	Approx. Time
Verbal Memory Test	The VBM test measures recognition memory for WORDS. Fifteen words are presented, one by one, on the screen every two seconds. For immediate recognition, the participant has to identify those words nested among fifteen new words. Then, after six more tests, there is a delayed recognition trial. Note: the VBM within CNS Vital Signs covers visual verbal memory while the HVLT-R covers auditory verbal memory.	3 minutes
Visual Memory Test	The VIM test measures recognition memory for FIGURES or SHAPES. Fifteen geometric figures	3 minutes

CNS vital sign tests and potential domains include (CNS Vital Signs):

	are presented, one by one, on the screen. For immediate recognition, the participant has to identify those figures nested among fifteen new figures. Then, after five more tests, there is a delayed recognition trial.	
Finger Tapping Test	The FTT requires subjects to press the Space Bar with their right index finger as many times as they can in 10 seconds. They do this once for practice, and then there are three test trials. The test is repeated with the left hand.	2 minutes
Symbol Digit Coding Test	The SDC test consists of serial presentations of screens, each of which contains a bank of eight symbols above and eight empty boxes below. The participant types in the number that corresponds to the symbol that is highlighted.	4 minutes

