# 11 Endpoints

# 11.1 Primary endpoint

## **Neurocognitive function**

Neurocognitive function (NCF) for the primary endpoint will be measured and assessed using the composite score of the EORTC core CTB COMP; consisting of HVLT-R, TMT-A/B and COWA. Neurocognitive assessments will be performed face-to-face on paper-based tests at baseline and 1, 12, 24, 36, 48 and 60 months post end of RT.

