# 12 Statistical Considerations

# 12.1 Sample size

The required sample size is 246 patients, recruited over 3½ years.

NCF is measured using CTB COMP, calculated from the mean of standardized z-scores for the HVLT-R, TMT-A/B, and COWA. The sample size for NCF at 5 years is based on a two-sample t-test. A Cohen's d of 0.5 is considered a moderate effect size (Cohen 1988); assuming a common standard deviation (SD) of 1 this effect size equates to a mean z-score of 0.5, and is deemed clinically relevant in this setting given that patients are typically young and of working age, so even small deteriorations will likely result in noticeable everyday issues (Giovagnoli and Boiardi 1994; Boele *et al.* 2014). This is the same targeted difference in CTB COMP score adopted in the NRG-BN005 US PBT vs. photon RT glioma study (NCT03180502) (NRG Oncology 2017). Based on a two-sample t-test with 5% two-sided significance and 90% power, 172 patients (86 per arm) are required to detect an effect size of 0.5. Assuming 30% loss to follow-up at 5 years (Cohen 1988; Klein 2019), 123 patients will be required per arm.

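### The face-to-face primary endpoint has no provision in the protocol for masking testers where feasible or recording whether they knew the arm, and the allocation email does not exclude them

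*Protocol*

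**What the plan says.** - **Design.** Protocol section 3: "APPROACH is a phase III UK multi-centre, open-label RCT with multi-staged assessments".
- **Mode of the primary endpoint.** Section 11.1: "Neurocognitive assessments will be performed face-to-face on paper-based tests at baseline and 1, 12, 24, 36, 48 and 60 months post end of RT". Section 9.10: "Tests within CTB COMP must be administered by a trained individual". The tests are HVLT-R, TMT-A/B and COWA.
- **Who tests.** Section 6.3, on the staff trained to give the tests: "These staff may be research nurses or other assigned healthcare professionals".
- **Who is told the arm.** Section 7.6, 24hour Randomisation: "Confirmation of randomisation, including details of treatment allocation, will be emailed automatically to the PI and research team once complete". No staff group is excepted.
- **Baseline.** Section 9.10: "Baseline testing must be completed before randomisation". Only the follow-up scores are therefore exposed.
- **Safeguards.** Testers are trained before the site opens and refreshed yearly (sections 6.3, 6.5 and 9.10). Completed forms go to the CTRU for QA and scoring, and "QA will be undertaken centrally through visual inspection of the raw data" (section 9.10). A second battery, CNS Vital Signs, is taken at the same visits and scored automatically (sections 9.10, 9.19 and 11.2).
- **Masking language.** The only such wording concerns committee reports: blinded safety data for the TSC and unblinded reports for the DMEC (sections 10.4 and 14.1).

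**The concern.** All the primary tests depend on an examiner. The tester reads the word list and takes down recall, times the trail making, and notes the words produced within a minute. A tester who knows the arm and expects protons to help can, without intending to, encourage more, prompt, or be generous with timing.

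Such a shift would arise only after randomisation and would differ by arm. It would enter the treatment contrast directly, and the baseline adjustment in section 13.4 would not remove it.

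Two decisions rest on this score: the 2-year result, which may change practice early, and the 5-year primary analysis. A positive 2-year result also releases the full 5% for the final test (section 13.3). The control of the family-wise error rate assumes that the measurement is unbiased.

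If awareness is not recorded, a later reader also has no direct means of seeing how far testing was unmasked in each arm.

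**Working it through.** **1. Is masking of testers possible at all?** Participants and treating clinicians cannot realistically be masked, because PBT is given at one of two national centres. Testers are in a different position. In both arms the participant is under the local centre during follow-up (section 8.1), and people who cannot attend follow-up there are excluded (section 4.2). The place of testing therefore does not reveal the arm, and nothing in section 9.10 requires the tester to know it. A site with more than one trained tester could use someone uninvolved.

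**2. Routes by which a tester can learn the arm**

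| Route | Protocol section |
|---|---|
| Automatic allocation email to the PI and research team | 7.6 |
| Photon RT given in the local department, PBT elsewhere | 3.1.1, 3.1.2 |
| Separate weekly treatment eCRFs for PBT and photon RT | 9.4 |
| PBT referral portal, completed by the PI or delegate | 3.1.2 |
| The participant, who knows the arm | follows from the open-label design, 3 |

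The email is one of five routes. Removing it alone would mask few testers.

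**3. The plan's own figures.** Section 12.1 targets d = 0.5 with SD 1: "Based on a two-sample t-test with 5% two-sided significance and 90% power, 172 patients (86 per arm) are required to detect an effect size of" that size. The two-sample t-test gives 85.03, so 86 per arm. With 30% loss, 86 / 0.70 = 122.9, so 123 per arm and 246 in total. Power at 86 per arm and a two-sided 4% level is 88.6% (stated as about 89%). At 2 years, 10% dropout leaves 123 x 0.90 = 110.7 per arm. Power at the 1% level is 86.5% with 110 per arm and 86.8% with 110.7 (stated as about 87%). All of these reproduce, and none is disputed.

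**4. Illustration of what a tester bias would do.** The documents give no bias figure. Assume no true effect and a shift of b SD towards PBT from all unmasked testing combined.

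SE = sqrt(2/n), d = b / SE, and P(reject) = 1 - Phi(z - d) + Phi(-z - d).

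- 5 years: n = 86, SE = sqrt(2/86) = 0.1525, two-sided 4%, z = 2.054.
- 2 years: n = 110, SE = sqrt(2/110) = 0.1348, two-sided 1%, z = 2.576.

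| Assumed b | d, 5 years | Type I error, 5 years (nominal 4%) | d, 2 years | Type I error, 2 years (nominal 1%) |
|---|---|---|---|---|
| 0.05 | 0.328 | 5.1% | 0.371 | 1.5% |
| 0.10 | 0.656 | 8.4% | 0.742 | 3.4% |
| 0.15 | 0.984 | 14.4% | 1.112 | 7.2% |

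Example for b = 0.10 at 5 years: 1 - Phi(2.054 - 0.656) + Phi(-2.054 - 0.656) = 0.0811 + 0.0034, about 8.4%.

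The non-central t distribution gives almost the same: 5.1%, 8.4% and 14.2% at 5 years; 1.5%, 3.3% and 7.1% at 2 years. The assumed shifts are 10% to 30% of the 0.5 SD target (0.05 / 0.5 and 0.15 / 0.5).

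**The case against.** The strongest reply is that the email is the wrong target. The trial is declared open-label, the site has to know the arm to arrange treatment, and a single notice at randomisation matters little against six weeks of local photon treatment and a participant who knows the arm for five years. This stands. A reader might infer from section 7.6 that the trial itself unmasks its primary assessors. The text does not go that far: it names the PI and research team, does not say that every tester is on the list, and section 6.3 allows testers to be other assigned professionals.

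A second reply is that the NCF test forms and the NCF administration and training guidelines are not shown. A reader might infer that tester awareness is recorded nowhere. That cannot be claimed. Only the protocol's own silence can be stated, although it cites those guidelines for administration and training, not for masking.

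Third, safeguards exist. Central scoring weakens the route through acceptance of answers. CNS Vital Signs is supervised but scored automatically, and gives a less examiner-dependent comparison, so it would be wrong to say that a shift could never be examined. What remains is prompting and timing, which inspection of returned forms cannot show.

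Fourth, the size and direction of the bias are assumed. That is correct, and the error rates in the table are not the cost of the email sentence.

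**Conclusion.** The point holds as a modest, worthwhile improvement. The protocol leaves an examiner-administered primary endpoint without any provision to mask testers where that is feasible or to record whether they knew the arm, and its allocation email makes no exception for them. The conclusion rests on the protocol text alone; a rule in the unseen NCF forms or guidelines could meet part of it, but would sit badly with section 7.6 if the testers also receive the email.

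The true size is unknown. Under an assumed shift of 0.05 to 0.15 SD towards PBT from all unmasked testing, with no true effect, the type I error would be about 5-14% instead of 4% at 5 years, and about 1.5-7% instead of 1% at 2 years. These figures show sensitivity, not an estimate of bias. The sample size and the open-label design are not in question.

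**What to change.** - **Section 9.10, choice of tester.** State that post-randomisation CTB COMP tests are given, where a site already has more than one trained tester, by one who is not involved in the participant's RT and has not been told the arm. Sites with a single tester continue as now.
- **Section 9.10, disclosure and recording.** Ask participants not to mention their arm to the tester. Record at each test whether the tester knew the allocation, unless the NCF forms already do so.
- **Section 7.6.** Leave those designated testers off the allocation email. The CTRU can identify them, because it already receives tester training evidence, the NCF Quality Assurance Log and the authorised personnel log (sections 6.3 and 6.6).
- **Analysis.** Report tester awareness by arm and run a supportive sensitivity analysis by awareness. State that this comparison is not randomised: awareness arises after allocation, may vary with site size, and the subgroups may be small.

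The cost is a change to an email list, one item on a form, one request to participants and one supportive analysis. No extra staff are needed. The downside is that masking will be partial and small sites will gain little.

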# 8 Trial Treatments

# 8.1 Radiotherapy

Radiotherapy will ideally start within 6 weeks of randomisation and must start within 10 weeks of randomisation.

Radiotherapy will also start within 21 days of the CT simulation scan.

An MRI, to assist in radiotherapy planning is required. This is ideally performed within 21 days, but must be performed within 28 days, of the CT simulation scan. The immediate post-operative MRI must NOT be used as a 'planning' MRI as immediate post-operative changes may not have had sufficient time to resolve.

For those randomised to photon RT, during photon RT, the participant will be under the care of the clinician in the local RT centre, who will be responsible for their radiotherapy planning, prescription and delivery. In the lead up to photon RT, during adjuvant chemotherapy and during follow up, the participant will be under the care of the clinician in the local centre.

For those randomised to PBT, during PBT, the participant will be under the care of the clinician in the PBT centre, who will be responsible for their radiotherapy planning, prescription and delivery. In the lead up to PBT, during adjuvant chemotherapy and during follow up, the participant will be under the care of the clinician in the local centre.

RT will be delivered as an outpatient on weekdays over approximately 6 weeks. Throughout this document the relative biological effectiveness (RBE) weighted dose in units of Gray(Gy(RBE)) is used to describe the product of the absorbed dose and the RBE. For PBT, the RBE should be interpreted as 1.1. For photons this should be interpreted as 1 for which Gy(RBE) is equivalent to the absorbed dose in Gy.

The total RT dose will be 54 Gy(RBE) in 30 daily fractions for grade II tumours and 59.4 Gy(RBE) in 33 daily fractions for grade III tumours. Radiotherapy will be delivered on weekdays over approximately 6 weeks (1.8 Gy per daily fraction for all)

Photon RT will be delivered using intensity modulated RT (IMRT) or rotational arc therapy. PBT will be delivered using pencil beam scanning with optimisation, typically performed using single field optimisation (SFO).

Please see the **APPROACH Radiotherapy outlining**, **planning**, **treatment delivery and quality assurance (QA) guidelines** for full details on immobilisation, image acquisition, outlining, planning, treatment delivery, treatment interruptions and quality assurance (QA).

All delineation will be performed at the treating centre.

Radiosensitizers should be discontinued prior to commencement of RT. Necessary washout periods should be discussed with local Pharmacy teams.

# 8.2 Chemotherapy

Adjuvant chemotherapy is as per standard of care and will consist of PCV (procarbazine, lomustine and vincristine).

### 8.2.1 Chemotherapy contraindications

# Patients with contra-indications to procarbazine or vincristine or lomustine must not be included in the trial.

Lomustine is contraindicated in patients with known hypersensitivity to the drug or any of its excipients, severe bone marrow depression or renal impairment, coeliac disease or wheat allergy. It is also contra-indicated in patients with the rare hereditary problems of galactose intolerance, total lactase deficiency or glucosegalactose malabsorption. Please refer to section 4.8 of the current approved version of the applicable summary of product characteristics (SMPC), supplied for use within the trial; (note this may not necessarily be the latest version of the SMPC).

Procarbazine is contra-indicated in patients with severe leucopenia or thrombocytopenia (from any cause), severe hepatic or renal disease and in patients with hypersensitivity to the active substance or any of its excipients. Please refer to section 4.8 of the current approved version of the applicable SMPC, supplied for use within the trial; (note this may not necessarily be the latest version of the SMPC).

Vincristine is contraindicated in patients with the demyelinating form of Charcot-Marie-Tooth Syndrome, childhood polio (CCO Formulary) or known allergy to vinca alkaloids or any of its excipients. Please refer to section 4.8 of the current approved version of the applicable SMPC, supplied for use within the trial; (note this may not necessarily be the latest version of the SMPC).

